13.7.1 Adverse Event Stopping Rule

The trial will be monitored closely for occurrence of adverse events by the study team and by the Mayo Clinic Cancer Center Data Safety and Monitoring Board (DSMB) using the adverse event (AE) stopping rule specified below during the first 2 parts of the study (i.e. first 57 weeks):

Adverse Event Stopping Rule: The stopping rule specified below is based on the knowledge available at study development. We note that the Adverse Event Stopping Rule may be adjusted in the event of either (1) the study re-opening to accrual after any temporary suspension or (2) at any time during the conduct of the trial and in consideration of newly acquired information regarding the adverse event profile of the treatment(s) under investigation. The study team in consultation with the Mayo DSMB may also choose to suspend accrual because of unexpected adverse event profiles that have not crossed the specified rule below.

Accrual will be temporarily suspended to this study if at any time we observe events considered at least possibly related to study treatment (i.e., an adverse event with attribute specified as "possible", "probable", or "definite") that satisfy any of the following criteria for each arm separately:

- If at any time 2 of the initial 10 treated participants or 20% of all participants (i.e. when accrual is greater than 10 participants) have experienced a grade 3 or higher adverse event.)
- Each grade 5 event will be reviewed on a case by case basis in a real time fashion to determine whether study accrual should be suspended. We will also review all grade 4 adverse events regardless of attribution to monitor the emergence of any previously unrecognized treatment related adverse event.

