2.3 Rationale

Completed Feasibility study of MUC1 Vaccine at U. of Pittsburgh

We enrolled 40 participants who received MUC1/Poly ICLC vaccine at 0, 2, and 10 weeks and antibody titers were evaluated prior to each vaccination and at week 12, 28 and 52³⁴. In the 39 participants that received all three initial doses of vaccine, 17 (44%) had over a two-fold ratio increase at week 12, ten participants had ratios over 4.5 fold, and another 4 participants had a ratio increase from 1.4 – 2.0. The kinetics of the response were similar, with peak antibody levels generally occurring after the third injection. As expected, circulating antibody levels tended to decline over the next year with clearance of the vaccine antigen.

Response to Booster vaccine

To test for the presence of a vaccine-induced T cell memory response, participants received a booster dose of vaccine at 1 year. Of the 16 participants who responded to the initial vaccination and received the booster, 12 (75%) had a two-fold ratio increase when comparing week 54 to week 52. Three of the 4 who didn't have a two-fold elevation at week 54 had maintained high levels of antibody at week 52, hence did not manifest a 2 fold ratio increase at week 54. Overall, the results suggest that responders established a T cell memory response to the MUC1 antigen.

Adverse Events

Over 150 vaccinations were administered in the pilot study. No adverse events above grade 1 were identified, and no unanticipated adverse events were observed. Most participants developed erythema with soreness at the injection site. Some developed short lived fever and muscle aches, which respond well to analgesics such as Tylenol. We had nearly 100% compliance with the study protocol. Participants were monitored with immunofluorescent ANA titers pre vaccination and at 1 year. No participants have developed a change in ANA titer and no new autoimmune diseases were observed.

Figure 2:

[figure not shown]

Figure 2A: Ratio response in MUC1 antibody.
Figure 2B: Kinetics of response to vaccination at 0, 2, and 10 weeks (arrows under x axis) and to booster vaccine at week 52.

Evaluation of Immune Non-Responders

Lack of response to vaccination was correlated with high levels of circulating myeloid-derived suppressor cells but not to circulating T regulatory cells.

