3.2 Study Design

This is a randomized, double-blind, placebo controlled phase II trial designed to elicit immune responses to abnormal MUC1. A 1-year booster vaccine will be administered to assess the presence of T cell dependent immune memory. Participants will be randomized on a 1:1 scheme. The protocol will call for injections at week T0, T2, and T10, and a booster injection at week T53. Monitoring of the immune response will be at each time point prior to injection, T0, T2, T10 and at week T12, T52, T55 (post booster), and at the time of the endpoint surveillance colonoscopy up to T156, for a total of 7 measurements of MUC1 immune response. For details regarding study visits and assessments, see Section 7.

Up to 120 participants will be approached for pre-registration, and assuming an 8% ineligibility rate, approximately 110 participants will be randomized to either vaccine or placebo injections and followed up to 3 years for the primary and secondary endpoints. A dropout rate of up to 10% is assumed between baseline and year 1, and an additional 10% drop out rate is assumed between year 1 and year 3 (termination of follow-up).

Eligible participants will have had an advanced adenoma that was completely resected as reported by endoscopic assessment. Advanced adenomas will be defined as: 1) ≥ 1 cm in size; 2) demonstrates villous or tubulovillous histology; or 3) have severe or high grade dysplasia. We anticipate enrolling approximately 4 participants per month across all sites for the first 3-6 months, and then 8 participants per month across all sites until we reach the accrual target. Accrual is expected to be completed in 18 months. Total study duration for Part 1 is expected to be about 22 months, followed by an additional 12 months for Part 2 and 24 months for Part 3.

Intervention Arms: Participants meeting study criteria will be randomly assigned to receive one of two interventions according to the following intervention schedule:

- Muc1/poly ICLC 0.3 mL subcutaneous study vaccine in the upper thigh
- Normal saline injection 0.3 mL subcutaneous in the upper thigh

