5.2 Vaccine Administration

The vaccine will be administered by appropriate site personnel subcutaneously in the anterior thigh approximately 20 cm inferior to the inguinal ligament. The vaccine will be administered into the same thigh on all 4 occasions for vaccine delivery. The vaccine site may demonstrate erythema after administration. This erythema can persist even to the timing of the next vaccine dosing. Erythema is not a contraindication to repeat vaccination. However, at the discretion of the investigator, repeat vaccination may be delayed, but not to exceed the protocol limits. It is also possible to inject the vaccine

into the opposite thigh, if necessary. Preferred windows for visits and vaccine administration and sampling are provided in Section 7.1.

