 12. The timing of the follow up surveillance colonoscopy will vary among individuals and institutions. Ideally, the participants will return at Week 156 (+/- 4 weeks) to update their medical/surgical history, concomitant medications, and immune response. If any clinical surveillance colonoscopies are scheduled between Weeks 52 and 156, it would be ideal to gather the updated med/surg history and concomitant medications within 2 weeks before the scheduled colonoscopies. If this is not possible, it will not be considered a protocol deviation. These data should still be gathered and the timing noted. Reports and specimens from the colonoscopy should be gathered within 30 days after the colonoscopy. Colonoscopy and pathology reports must be submitted by FAX or email to the CPN Quality Assurance Specialist (QAS) within 30 days after the date of the procedure.

Summary of Parameters for Visit Timing

Week/Visit	Window	Ideal timing
0	Within 28 days of screening visit	within 1 week
2	No earlier than 2 weeks and up to 4 weeks from week 0 injection	2 weeks from week 0 injection
10	7 – 10 weeks from week 2 injection	8 weeks from week 2 injection
12	10 – 21 days after week 10 injection	2 weeks from week 10 injection
52	51 to 54 weeks from week 0 injection	52 weeks
53	As soon as possible after week 52 monitoring tests return	Within 4 weeks of week 52 visit
55	10 – 21 days from week 53 injection	2 weeks
156	Within 4 weeks of any planned colonoscopy	2 weeks before colonoscopy

Note: If the visit/event takes place within the window specified above, it will not be considered a deviation. However, for consistency, every effort should be made to schedule visits and events according to the “ideal timing” column. The scheduling of subsequent injections should be based on timing of previous injection. If sampling or injections are delayed, they should still occur (even after colonoscopy for week 156 titer, for example), and timing should be noted.

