12.4 Data and Safety Monitoring Plan

The Master DSMP, applicable to all studies within the CPN Consortium provides detailed information regarding data and safety monitoring for this study. The trial will be monitored closely for occurrence of adverse events by the study team and by the Mayo Clinic Cancer Center Data Safety Monitoring Board (DSMB). The DSMB will be consulted regarding whether or not accrual should be suspended to allow for investigation in the occurrence of severe adverse events, particularly for those that are possibly, probably, or definitely related to the study agent.

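### The adverse-event stopping rule runs through the week-53 booster, but the only action it states on a crossing is to suspend accrual; nothing supplied ties a crossing to holding injections in enrolled participants

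*Combined protocol and SAP*

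**What the plan says.** Section 13.7.1 has the study team and the DSMB apply the rule "during the first 2 parts of the study (i.e. first 57 weeks"). Injections fall at weeks 0, 2, 10 and 53 (Section 7.3), and the Parts I and II schedule in Section 7.1 ends at each participant's week 57, so the booster is inside the monitored period.

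The limit is 2 of the first 10 treated, or 20% of participants after that, with an at least possibly related grade 3 or higher event, counted in each arm separately. The action is: "Accrual will be temporarily suspended to this study if at any time we observe events considered at least possibly related to study treatment".

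The surrounding provisions are framed the same way:

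- Grade 5 events are reviewed case by case "to determine whether study accrual should be suspended".
- The discretion to act before the limit is reached is a discretion to suspend accrual.
- Grade 4 events are reviewed, with no action named.
- Section 12.4: "The DSMB will be consulted regarding whether or not accrual should be suspended".

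On timing, Section 3.2 states: "Accrual is expected to be completed in 18 months". On late doses, Section 7.1 states: "If sampling or injections are delayed, they should still occur".

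**The concern.** The rule outlasts its only stated action. Suspending accrual protects people who have not yet entered. The people most exposed to an emerging toxicity are those due another dose of the same agent, and for them the rule as written changes nothing. After the last participant is randomized, a crossing triggers an action that can no longer do anything, although the rule is still meant to be running.

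Participants are at raised risk of colorectal neoplasia but, in the protocol's own terms, otherwise healthy (Section 13.1), and the intervention is preventive. A pre-specified safety limit is there so that the first response to a signal does not have to be improvised. Here that response is specified only for future entrants.

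**Working it through.** **Inputs.** About 110 randomized from 120 screened, 55 per arm (Section 13.3). Accrual of 4 per month for 3-6 months, then 8 per month (Section 3.2). Injections at weeks 0, 2, 10 and 53. Pilot: 40 participants, and "No adverse events above grade 1 were identified" (Section 2.3). Assumptions: steady enrolment within each period, 1:1 allocation, no dropout, week 0 at randomization. With 52.1775/12 weeks per month, week 2 is 0.46 months, week 10 is 2.30 and week 53 is 12.19.

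**1. Accrual time.** Months = ramp + (N − 4 × ramp)/8.

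- N = 120, 6-month ramp: 6 + 96/8 = 18.0. This reproduces the stated 18 months.
- N = 110, 3-month ramp: 3 + 98/8 = 15.25.
- N = 110, 6-month ramp: 6 + 86/8 = 16.75.

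**2. Boosters still due when accrual closes.** These belong to everyone enrolled in the last 12.19 months.

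| Accrual pattern (N = 110) | Enrolled more than 12.19 months before close | Boosters due after close | Share |
|---|---|---|---|
| 3-month ramp, closes at 15.25 | 12 + 8 × 0.06 = 12.5 | 97.5 | 89% |
| 6-month ramp, closes at 16.75 | 4 × 4.56 = 18.2 | 91.8 | 83% |
| Uniform over 18 months | 110 × 5.81/18 = 35.5 | 74.5 | 68% |

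Half of these are in the vaccine arm: about 37-49 of 55.

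**3. Doses outstanding if the vaccine arm crosses with 20 randomized (10 vaccine).**

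- 6-month ramp, month 5: week-10 doses outstanding 4 × 2.30 = 9.2, week-2 doses 4 × 0.46 = 1.8. Vaccine arm: (9.2 + 1.8)/2 = 5.5.
- 3-month ramp, month 4: week-10 doses 20 − 4 × 1.70 = 13.2, week-2 doses 8 × 0.46 = 3.7. Vaccine arm: (13.2 + 3.7)/2, or about 8.4.

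So about 6-8 injections are due within weeks. All 10 vaccine-arm boosters are also outstanding, but the first is due no sooner than 12.19 − 5 = 7.2 months later.

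**4. Chance of a crossing in one arm.** Binomial, independent participants, p = true rate of related grade 3 or higher events per participant over the 57 weeks. The 7.2% row is the one-sided 95% upper bound from 0 of 40 in the pilot: 1 − 0.05^(1/40) = 0.072.

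| p | ≥ 2 of first 10 | ≥ 11 of 55 | ≥ 11 of 55 with ≤ 1 in the first 10 |
|---|---|---|---|
| 2% | 0.02 | < 0.0001 | < 0.0001 |
| 5% | 0.09 | < 0.0001 | < 0.0001 |
| 7.2% | 0.16 | 0.0017 | 0.0006 |
| 10% | 0.26 | 0.019 | 0.006 |
| 15% | 0.46 | 0.19 | 0.06 |

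The last column is P(0 of 10) × P(≥ 11 of 45) + P(1 of 10) × P(≥ 10 of 45). It is an upper limit for a first crossing at full enrolment, because paths that pass 20% at an intermediate count would already have crossed. The 2-of-10 column uses full follow-up of the first 10; by month 4-5 the chance is lower, and a later crossing finds more people enrolled.

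**The case against.** The strongest reply is that enrolled participants are not left without protection, and this is correct. Every serious event goes to the DCP Medical Monitor by phone within 24 hours and in writing within 48 (Section 11.2.2). The sponsor and the FDA can stop the study at any time (Section 8.5). A participant can come off agent for an adverse event (Section 8.3). Each booster is scheduled after the week-52 examination and laboratory tests (Section 7.1). The DSMB monitors throughout, the rule may be adjusted at any time, and nothing confines the DSMB to advice on accrual once it is investigating. A reader might infer from Section 13.7.1 that dosing could not be stopped, or that nobody would look; the documents do not support that. What stands is narrower: each of these routes is discretionary or acts on one participant, and none is a stated dosing action on a crossing.

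Second, Section 12.4 refers to a Master DSMP for the detail of safety monitoring. It was not supplied and may contain a dosing hold, so the gap is shown only for the supplied text.

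Third, the size is modest. Early in the trial most outstanding doses are boosters months away, which leaves the DSMB time to act. A first crossing after accrual has closed is remote at rates the pilot supports.

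Fourth, a hold has its own costs, set out with the fix.

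**Conclusion.** The point holds as a mismatch between the rule's stated period and its stated action. On the supplied text, a crossing suspends accrual and leaves enrolled participants' injections on schedule; after closure, with 68-89% of boosters still due, the stated action does nothing.

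The case that matters in practice is an early crossing, with probability about 0.02 to 0.46 over true rates of 2% to 15% and about 6-8 near-term vaccine-arm injections at stake when 20 are randomized. It would be tempting to put the main weight on the many boosters given after closure, but a first crossing only at 11 of 55 has probability at most about 0.0006, 0.006 and 0.06 at 7.2%, 10% and 15%.

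These figures rest on steady accrual, no dropout and independent binomial events. The textual finding does not depend on them. Nothing here affects the primary comparison of IgG ratios. It is a cheap patient-safety improvement that should be made; confidence is medium because the Master DSMP was not available.

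**What to change.** Amend Section 13.7.1 so that a crossing (a) suspends accrual if it is open and (b) temporarily holds further study injections in enrolled participants, in both arms to protect the blind, pending prompt DSMB review. The DSMB decides whether dosing resumes. Align the DSMB question in Section 12.4. State that doses delayed by a hold are given late with the timing noted, as Section 7.1 already allows, and that the limit in Section 5.2 ("repeat vaccination may be delayed, but not to exceed the protocol limits") does not apply to them. If the Master DSMP already sets a dosing hold, a cross-reference in 13.7.1 is enough.

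Cost: protocol wording and DSMB agreement, with no added participants or routine procedures. Downsides: some doses may fall outside their windows (week 10 is due 7-10 weeks after week 2); a long hold widens the gap between the week-52 titer and the booster and so affects T55/T52; and a crossing in the placebo arm alone would also pause vaccine doses. Prompt review keeps these small.

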13.8 Evaluation of Response

All randomized participants who are evaluated at week 0 and week 12 and have IgG values from those timepoints will be evaluable for the primary endpoint of this study using the intent-to-treat principle. All conclusions regarding efficacy will be based on all participants who completed both week 0 and week 12 and have IgG values from those timepoints as well. Subanalyses may be performed on the subsets of participants, excluding those for whom major protocol deviations have been identified (e.g., early death due to other reasons, early discontinuation of intervention, major protocol violations, etc.). However,

sub-analyses may not serve as the basis for drawing conclusions concerning efficacy, and the reasons for excluding participants from the analysis should be clearly reported. For all measurements of response (i.e. the primary endpoint), the 95% confidence intervals will also be provided.

13.9 Interim Analyses

Part I: The Part 1 primary endpoint analysis will be the first interim analysis. If the MUC1 vaccine is shown to significantly increase the IgG ratio as compared to placebo, we will move into the Part 2 portion of the study. This is defined in detail in Section 13.4.

Part II: If the booster vaccine shows a significant increase in the 1-year immune response as compared to placebo and the response rate exceeds 15%, we can proceed to Part III.

Study enrollment and implementation will not be halted for these analyses unless the results indicate that the study should not proceed to the next Part.

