3.3 Vaccine and Clinical Endpoints

The response to the vaccine will be evaluated by monitoring changes in IgG anti-MUC1 antibody titer ratio; defined as t_{12}/t_0 , where t_0 is the "initial titer" measured prior to vaccination, and t_{12} is the "final titer" drawn at 12 weeks. For the primary endpoint, the titer measured 2 weeks after the 3rd vaccination, at week 12, will be compared to the baseline titer at week 0. Because IgG is more commonly induced and more likely to be detected because of the better quality of reagents, IgG levels will be the indicator of immunogenicity. A titer ratio of ≥ 2 will be considered an immune response. The use of a titer ratio permits a uniform definition for an immunologic response regardless of the baseline level of MUC1 antibody. The titer ratio at week 12 will mark the close of Part 1 of the trial. The assessment of the response to the booster vaccine will be evaluated by examining the week 55 titer to the titer at week 52, prior to receipt of the booster vaccine. Once again, a titer ratio of ≥ 2 for the T55/T52 comparison will be considered a positive immune response.

The titer ratio of 2:1 as a measure of immune response was chosen in part from the infectious disease literature where this ratio is often employed as a marker of immune response. This ratio was commonly attained (44%) in our pilot study in participants with advanced adenoma³⁴. A titer increase of ≤ 2 may also have clinical efficacy. We have no preliminary information to identify what titer ratio may be associated with a clinical endpoint. The measurement of the response to the booster vaccine and communication with the patient regarding response (week 55) will mark the close of Part 2 of the trial.

The week 156 endpoint will be adenoma recurrence. Adenoma prevention trials testing chemoprevention regimens have been performed for a variety of compounds ranging from beta carotene, calcium, folate, aspirin, DFMO, dietary modification, fiber supplementation, etc. Although there have been repeated calls for trials using other intermediate endpoints such as aberrant crypt foci, adenoma recurrence remains the mainstay in examining the efficacy of an agent in relation to colorectal cancer. The adenoma is a reproducible measure, with a reproducible, standardized nomenclature implemented by pathologists.

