13.4 Primary Objective, Endpoint, Analysis Plan

The primary objective for this study is to compare the ratio of the week 12 to week 0 IgG levels between the MUC1 vaccine and placebo. It is hypothesized that this ratio will be increased in patients treated with the MUC1 vaccine as compared to patients receiving the placebo. Prior data from a pilot study of 39 patients that were treated with the MUC1 vaccine³⁷ showed a mean IgG ratio of 6.46 with a standard deviation of about 10. Assuming equal standard deviations (i.e. 10) across the MUC1 and placebo groups, and assuming up to a 10% drop-out rate by year 1 (presumably less by 12 weeks), retaining at least 50 evaluable participants per arm yields at least 86% power to detect an increase in the mean IgG ratio from 1 to 6.5 for placebo vs. MUC1 (effect size = 0.55), using a 1-sided t-test with a significance level of 0.05. If the data are not normally distributed, we will use the Wilcoxon Rank-Sum test for this primary endpoint analysis. If the vaccine shows a significant increase in the 12-week immune response rate as compared to placebo, we will proceed to Part 2.

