13.5 Secondary Objectives, Endpoints, Analysis Plans

As discussed previously, there will be key powered secondary endpoints for this study across all 3 parts.

1) Immune response at 12 weeks (Part 1): The key secondary endpoint for Part 1 will compare the proportion of patients that have at least a 2-fold increase in the IgG ratio (week 12/week 0) between MUC1 and placebo. Based on the pilot study³⁷, we hypothesize that around 40% of vaccinated participants will demonstrate a 2 fold increase in MUC1 titer at week 12 compared to around 10% for the placebo arm. Assuming a drop-out rate of up to 10% by 1 year (presumably less by 12 weeks), retaining at least 50 evaluable participants per arm provides 94% power to detect an increase in the 12-week immune response rate from 10 to 40%, assuming a 2-sided significance level of 0.05 (nQuery Advisor 6.01).

2) Booster Response at 1 year (Part 2): The key secondary endpoint for Part 2 will assess the booster response at week 55 vs. week 52 for the vaccine as compared to placebo. Based on the pilot study, we expect 75% of week-12 responders will respond with a doubling of MUC1 antibody levels, or about 35% of the overall sample. We expect the 1-year response rate to be around 10% in the placebo group. Of the 110 randomized participants (55/arm), we expect that up to 10% will drop out by 1 year, leaving

approximately 100 participants evaluable for this analysis (50/arm). With 50 evaluable participants per arm, we would have 92% power to detect an increase in the 1-year immune response rate from 10 to 35%, assuming a 1-sided significance level of 0.05 (nQuery Advisor 6.01). We will also compare the actual IgG ratio values between the 2 treatment arms as well. If the booster vaccine shows a significant increase in the 1-year immune response as compared to placebo and a response rate that exceeds 15%, we can proceed to Part III.

3) Adenoma recurrence rate at 3 years (Part 3): Part 3 will evaluate the adenoma recurrence rate at least one year and up to 3 years. The adenoma recurrence rate at 3 years in participants with an adenoma is generally around 40-50%³³. Assuming an additional 10% drop out rate between years 1 and 3, we will have 90 participants (45/arm) evaluable for this endpoint, which will provide >80% power for the different effect sizes shown in the table below (1-sided alpha = 0.05).

# Evaluable	Effect Size (delta)	Power	1-sided alpha
90 (45/arm)	50 vs. 25%	79%	0.05
90 (45/arm)	45 vs. 20%	82%	0.05

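### Sections 13.4 and 13.9 state different go rules for Part 2: one uses the 2-fold response rate, the other the IgG ratio

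*Combined protocol and SAP*

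**What the plan says.** Section 13.9 makes the Part 1 primary endpoint analysis the first interim analysis and gives the rule: "If the MUC1 vaccine is shown to significantly increase the IgG ratio as compared to placebo, we will move into the Part 2 portion". It adds: "This is defined in detail in Section 13.4".

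Section 13.4 sets out the primary analysis of the week 12 to week 0 IgG ratio, "using a 1-sided t-test with a significance level of 0.05. If the data are not normally distributed, we will use the Wilcoxon Rank-Sum test". It closes with the go rule: "If the vaccine shows a significant increase in the 12-week immune response rate as compared to placebo, we will proceed to Part 2".

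The term in that last sentence has a meaning elsewhere in the document. Section 3.3 says: "A titer ratio of ≥ 2 will be considered an immune response". Section 13.5 item 1, on the proportion with at least a 2-fold increase, states "94% power to detect an increase in the 12-week immune response rate from 10 to 40%, assuming a 2-sided significance level of 0.05". Section 8.2 lists that proportion as the Part I key secondary endpoint.

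**The concern.** The section that 13.9 names as the authority carries a different rule from 13.9 itself. The endpoint differs (a continuous ratio against a proportion), and so does the planned sidedness. The gate sentence in 13.4 states no alpha; the two-sided 0.05 comes from the power statement in 13.5.

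At stake is the decision to continue. Part 1 is planned to read out at about month 22. A booster at week 53 falls about 12.2 months after the first injection, so participants who started by month 22 - 12.2 = 9.8 are due by then. With even accrual over 18 months that is 9.8/18 × 110 ≈ 60 boosters due and about 50 outstanding. Across even and ramped accrual, a booster at week 53 or 58, and a read at month 22 or 4 months after accrual closes, 44 to 75 of 110 remain, before dropout. If one rule is met and the other is not, the text lets either be followed once the results are known.

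**Working it through.** **1. The two rules side by side**

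| | 13.9 | 13.4, last sentence |
|---|---|---|
| Quantity | IgG ratio, week 12 / week 0 | 12-week immune response rate (ratio ≥ 2) |
| Endpoint status | Primary | Key secondary (8.2) |
| Test | t-test, or Wilcoxon if not normal | None named; a comparison of proportions |
| Alpha | One-sided 0.05 | None in the sentence; two-sided 0.05 in 13.5 |

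**2. The plan's own power figures (50 per arm)**

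- IgG ratio, mean 1 vs 6.5, SD 10: noncentrality 0.55 × √(50/2) = 2.75. Normal approximation Φ(2.75 - 1.645) = 86.5%; noncentral t gives 86.1%. Stated: at least 86%.
- Response rate, 10% vs 40%, two-sided 0.05: pooled p = 0.25, SE0 = √(2 × 0.25 × 0.75/50) = 0.0866, SE1 = √((0.09 + 0.24)/50) = 0.0812. Then (0.30 - 1.96 × 0.0866)/0.0812 = 1.60 and Φ = 94.6%. Stated: 94%.

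Both reproduce. They are separate tests, and each can pass without the other.

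**3. How often the rules disagree**

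The documents give the pilot mean (6.46) and SD (about 10) in 13.4, the pilot count of 17 of 39 over 2-fold in 2.3, and the planned 40% vs 10% in 13.5. They give no distribution. Assumed, with 20,000 simulated trials of 50 per arm:

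- Placebo: lognormal with 10% at or above 2. With median 1, the log-SD is ln 2/1.282 = 0.54. Model B was also run with mean 1.
- Vaccine: a share p respond; the rest follow the placebo distribution below 2.
- Model A: responders are 2 + lognormal, with mean 14.66 and SD 11.73 at p = 40%. The arm mean is 0.40 × 14.66 + 0.60 × 0.99 = 6.46, and the arm SD is 10.
- Model B: responders are 2 + exponential, scaled so that p = 44% gives mean 6.46 and SD about 10.
- Ratio gate: t-test or Wilcoxon, one-sided 0.05. Rate gate: Fisher or chi-square, one- or two-sided 0.05 (A); two-proportion test, two-sided 0.05 (B).

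Share of trials in which the two gates give opposite decisions:

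| Vaccine response (placebo 10%) | t-test vs rate | Wilcoxon vs rate |
|---|---|---|
| 44% (A) | 0.7-3.0% | 4.2-5.0% |
| 40% (A) | 2.4-7.2% | 8.3-9.3% |
| 40% (B) | 4.6-4.8% | 9.3-9.6% |
| 30% (B) | 26.1-26.2% | 26.2-26.6% |
| 25% (B) | 43.5-44.8% | 29.1-30.2% |

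Pass rates in model B (t / Wilcoxon / rate): 1.00 / 0.90 / 0.95 at 40%; 0.99 / 0.63 / 0.73 at 30%; 0.97-0.98 / 0.43-0.44 / 0.53-0.54 at 25%. With the t-test, the ratio gate passes more often than the rate gate. With the Wilcoxon, the usual conflict is the reverse: the rate passes and the ratio fails (7.2-7.7% of trials at 40%).

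**4. Other distributions**

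- Normal, SD 10 in both arms, as in the power calculation: 18-35% disagreement. This model puts 67% and 46% of the arms at or above 2, not 40% and 10%.
- Lognormal vaccine arm matched only to mean 6.46 and SD 10: about 0%. It implies about 70% responders.
- Single lognormal vaccine arm with 40% responders, log-SD 0.54 to 1.5: 2-10% (t-test), 2-59% (Wilcoxon).

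In the pilot 22 of 39 did not exceed 2-fold, so the median was at most 2 against a mean of 6.46. That strong skew fits a mixture better than the first two alternatives, and it makes the Wilcoxon fallback likely.

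**The case against.** The strongest reply is that 13.4 is loosely worded. Its last sentence closes the section on the primary endpoint, directly after the primary test. Section 13.9 names the primary endpoint analysis as the interim, and 13.1 lists the ratio as the Part I key endpoint. This is probably the intent, and the fix follows it. But the text does not settle it: 13.5 uses the same term for the 2-fold proportion, 8.2 gives that proportion key status, and the Part II gate is itself built on a response rate.

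It is also fair to say that neither reading inflates the type I error of the primary test, which is done once at its own alpha. That stands. The point concerns the continuation decision, and no printed power figure is challenged.

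A reader might go further and infer that nothing is said about a Part II miss. The documents do not support this. The last sentence of 13.9 covers both interim analyses: "Study enrollment and implementation will not be halted for these analyses unless the results indicate that the study should not proceed to the next Part". Section 13.1 has all patients followed for recurrence, and 7.5 continues contact to week 156 or reported recurrence. There is some tension between the implied halt and that follow-up, but it is not a missing rule. Nor is the arm for the 15% threshold unstated: 13.5 reads "If the booster vaccine shows a significant increase in the 1-year immune response as compared to placebo and a response rate that exceeds 15" (percent), which attaches the rate to the booster vaccine.

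**Conclusion.** The two go rules for Part 2 are incompatible as written, and the cross-reference from 13.9 to 13.4 leads to the conflict instead of resolving it. This rests on the text alone.

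The size does depend on assumptions. In the mixture matched to the pilot, the conflict rate is roughly 2-7% (t-test) or 8-10% (Wilcoxon) at 40% vs 10%. It rises to about 25-45% if the vaccine response is 25-30%, which is where a gate matters most. Across the other distributions tried it runs from about 0% to 59%. A reader might take a single figure near 9-10% as a property of the plan. It belongs to one model with the Wilcoxon; the t-test, the planned first choice, gives less at the planned response.

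The wording should be corrected. The Part II tension is a matter for optional clarification only.

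**What to change.** In the last sentence of 13.4, replace *12-week immune response rate* with *IgG ratio (primary analysis, one-sided 0.05)*. Sections 13.4 and 13.9 then gate on the same primary endpoint and the cross-reference works. Sample size, alpha, visits and injections do not change.

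The cost is small and depends on the test. In the mixture model, the Wilcoxon gate on the ratio passes about 5 points less often than the response-rate gate at the planned response (90% vs 95%), and about 10 points less often at a 25-30% response. With the t-test it passes more often.

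Optionally, one sentence in 13.9 could reconcile the implied halt after a Part II miss with the statement in 13.1 that all patients are followed for recurrence.
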